**The product of IGA and BSA will not be summarized for the OLE2 treatment period.**

### Change #35

**Section 8.3.5 Dermatology Life Quality Index (DLQI).** The following texts in bold have been added

The DLQI related efficacy variables will be summarized for the double-blind treatment visits separately for the RS and MS, and **separately for OLS and OLS2 [DLQI(0/1) only]** by treatment sequence respectively and visit

### Change #36

**Section 8.3.8 Symptoms of PSO (Itch, pain, and scaling).** The following texts in bold have been added

Cumulative distribution plots will also be provided for absolute change from Baseline PSD at Week 16 and Week 48 for each item

**Listings of response to individual question of the patient diary will be provided separately for the Initial, Maintenance, OLE, and the OLE2 treatment periods.**

**Summaries of PSD responder to Itch, Pain, and scaling symptoms will be produced for the OLE2 by treatment sequence as described in Section 3.6.**

### Change #37

**Section 9: PHARMACOKINETICS AND PHARMACODYNAMICS** The following treatment sequences and texts (in bold) have been added:

**For the Week 48 Interim the following treatment groups were summarized for the Initial and Maintenance Treatment Period.**

**Bimekizumab 320mg Q4W/Q8W with switch from Q4W to Q8W occurring at Week 16**  
**Bimekizumab 320mg Q4W.**

**PK and ADAb will also be summarized through to Week 144 by the following treatment sequence and by visit for Initial, Maintenance, and Open-Label Extension treatment period combined. No PK or ADAb samples will be collected in the OLE2 treatment period.**

- **Subjects receiving bimekizumab in the double-blind treatment period until treatment discontinuation:**
  - **Bimekizumab 320mg Q4W/Q8W with switch from Q4W to Q8W occurring at Week 16**
  - **Bimekizumab 320mg Q4W/Q8W with switch from Q4W to Q8W occurring at Week 48**
  - **Bimekizumab 320mg Q4W/Q8W with switch from Q4W to Q8W occurring at Week 72 or 84**

- **Bimekizumab 320mg Q4W/Q8W with switch from Q4W to Q8W occurring at Week 96 or later**
- **Bimekizumab Total (only for immunogenicity analyses).**

Subjects with any other treatment sequence groups (eg, Bimekizumab 320mg Q4W/Q8W/Q4W or Q4W/Q8W/Q4W/Q8W) will be allocated the "Bimekizumab Total" treatment sequence group for immunogenicity analysis only. All data will be included in the listings.

- **Subjects receiving secukinumab in the double-blind treatment period:**
  - **Bimekizumab 320mg Q8W from Week 48**
  - **Bimekizumab 320mg Q4W/Q8W with switch from Q4W to Q8W occurring at Week 72 or 84**
  - **Bimekizumab 320mg Q4W/Q8W with switch from Q4W to Q8W occurring at Week 96 or later**
  - **Bimekizumab Total (only for immunogenicity analyses)**

Note that subjects who received Bimekizumab 320mg Q4W only, ie, those who discontinued before switching to Q8W, will be allocated to the corresponding Q4W/Q8W treatment sequence group depending on when the subject discontinued. For example, if a subject discontinued at week 68, they will be allocated to group Bimekizumab 320mg Q4W/Q8W, switch occurring at Week 72 for PK summary table and figure purposes.

### Change #38

**Section 9.3 Immunogenicity.** The following texts in bold have been added.

The analysis of immunogenicity **for the Week 48 Interim** will be based on the SS **All other analyses will be based on the BKZ Set.**

### Change #39

**Section 9.3.2: Anti-bimekizumab antibodies**

The following texts (in bold) have been added:

Anti-bimekizumab antibodies will be measured using a three tiered assay approach: screening assay, confirmatory assay and titration assay. Samples confirmed as positive within the confirmatory assay, will be further evaluated in a neutralizing assay to evaluate the potential of the ADAb to neutralize the activity of Bimekizumab (IL17A or IL17F, or both) in-vitro. Samples were taken at baseline, week 1, week 2, week 4, week 8, week 12, week 16, week 20, week 24, week 36, week 48, Week 72, Week 96, Week 120, Week144 (or PEOT) and at SFU which is 20 weeks after the last dose. **Due to the planned entry of some subjects to the OLE2 period, not all subjects will have an SFU period immediately following Week 144 with PK and immunogenicity samples.**

If the titer for an ADAb level that is positive screen and positive immunodepletion is missing, then a conservative approach will be used and ADAb status will be considered as positive. No imputation rules apply for the missing titer. If the ADAb level is positive screen but no confirmatory result could be determined, then a conservative approach will be used and ADAb status will be considered as positive.

Anomalous values will be not included in summaries/analysis and will be reviewed and flagged by pharmacokinetic expert.

For each subject an overall ADAb status in the treatment period (Baseline to Week 144) will be derived:

- Overall Positive is defined as having at least one value that is confirmed positive during the treatment period.
- Overall Negative is defined as having no values that are confirmed positive at any time up to Week 144 and at least 2/3 of the protocol scheduled post-baseline assessments up to Week 144 are evaluable (i.e. neither missing as per schedule nor inconclusive)
- Overall Missing is defined as having no values that are confirmed positive at any visit in the treatment period, but the subject has 1/3 or more protocol scheduled post-baseline assessments missing (or inconclusive) up to Week 144.

This differs from the Week 48 interim analysis where all subjects were defined as either overall positive or overall negative only (a missing category was not considered). As the time on treatment is protracted in this open label extension study (up to 144 Weeks), missing data or subject discontinuation may be more prevalent and is therefore considered for the final analysis

The double-blind and OLE treatment periods do not include Baseline/pre-treatment samples or SFU.

Furthermore, the following subcategories for each subject will be derived:

1. Pre anti-bimekizumab antibody negative – treatment emergent anti-bimekizumab antibody negative: Includes subjects who are negative at Baseline and antibody negative at all sampling points post treatment (excluding SFU)
2. Pre anti-bimekizumab antibody negative – treatment emergent anti-bimekizumab antibody positive: Includes subjects who are negative at Baseline and antibody positive at any sampling point post treatment (excluding SFU). This group also includes subjects who have a missing pre-treatment sample (either missing or insufficient volume) at Baseline with one or more anti-bimekizumab antibody positive post-treatment samples.
3. Pre anti-bimekizumab antibody positive – treatment emergent reduced anti-bimekizumab antibody: Includes subjects who are positive at Baseline, and antibody negative at all sampling points post treatment (excluding SFU).
4. Pre anti-bimekizumab antibody positive – treatment emergent unaffected anti-bimekizumab antibody positive: Includes subjects who are positive at Baseline and are positive at any sampling point post treatment (excluding SFU) with titer values

of the same magnitude as Baseline (ie, less than a 2.07 fold difference from the Baseline value).

5. **Pre anti-bimekizumab antibody positive – treatment emergent anti-bimekizumab antibody boosted positive:** Includes subjects who are positive at Baseline and are positive at any sampling point post treatment (excluding SFU) with increased titer values compared to baseline (greater than a 2.07 fold difference increase from Baseline value which will be defined within the validation of the assay).
6. **Inconclusive:** Includes subjects who have a positive pre-treatment sample and some post-treatment samples are missing, while other post-treatment samples are anti-bimekizumab antibody negative.
7. **Total treatment-emergent ADAb positivity (Category 7 [Categories 2 and 5 combined]):** Includes study participants who are pre ADAb negative – treatment-emergent ADAb positive (Category 2) and pre ADAb positive – treatment boosted ADAb positive (Category 5).
8. **Total prevalence of pre- ADAb positivity (Category 8 [Categories 3, 4 and 5 combined]):** Study participants that are tested ADAb positive at Baseline.
9. **Missing:** Includes subjects who are antibody negative at baseline, are not positive at any post-baseline visit, and have at least one missing post-treatment scheduled assessment. Note this is also applicable to subjects who have missing baseline.

For the Week 144 analysis, when all OLE and SFU data will be available, data from the OLE and SFU visits will be considered. That is, each instance of “excluding SFU” in the categories above, should be changed to “including SFU.”

In the case that a sample is collected one or more days following the scheduled visit date in which the drug was administered, the anti-bimekizumab antibody results for that sample will be associated with the scheduled visit and summarized accordingly. Such samples will also be considered when anti-bimekizumab antibody results are summarized over a given study period.

#### Analysis

- Immunogenicity will be assessed through summary tables, figures, and listing of individual results by subject. **The analysis of immunogenicity will be summarized by treatment sequence as described in Section 9 and visit.** All analyses will be run on the safety population, unless specified otherwise. Summary of anti-bimekizumab antibody status overall and by each visit separated by treatment **sequence**
- Summary of the time-point of the first occurrence of anti-bimekizumab antibody positivity during the treatment period by treatment **sequence**. A plot of the titer by time to first anti-bimekizumab antibody positivity will be prepared.
- All individual subject-level anti-bimekizumab antibody results will be listed.
- The number and percentage of subject in each of the **8** anti-bimekizumab antibody categories during the treatment period by treatment **sequence**, with an additional category combining subjects in categories 2 and 5, summarized as total treatment emergent. In addition, the count

and percentage of subjects who are pre anti-bimekizumab positive will be calculated (this is the sum of categories 3, 4, and 5).

- The prevalence of immunogenicity, separated by treatment **sequence**, and defined subcategory, will be reported by visit, defined as (cumulative) proportion of subjects having confirmed positive anti-bimekizumab antibody samples at any visit up to and including that visit. Missing samples will not be included in the denominator.
- The time to achieving treatment-emergent anti-bimekizumab antibody positivity, separated by treatment **sequence** and defined sub-category, will be analyzed based on Kaplan-Meier methods. Subjects will be considered to have an event at the time point at which treatment emergent anti-bimekizumab antibody positive is first achieved. Subjects classified as treatment-emergent anti-bimekizumab antibody negative will be censored at the time of the last available anti-bimekizumab antibody result.
- A summary of PASI 100 responders, separated by treatment sequence and defined sub-category, at weeks 16 and 48 as a function of ADAb titer will be presented graphically. This will be repeated for PASI 75 and 90 responders.
- Individual plots of Bimekizumab Concentrations/ anti-bimekizumab antibody titer and PASI score all plotted on the Y-axes by visit (x-axis) for the full treatment period (excluding SFU and OLE period for interim analyses and including SFU and OLE period for final analyses), where a patient has not progressed into the OLE. Plots should be labeled and grouped into the 7 sub-categories.
- Spaghetti plots of ADAb titer (y-axis) by visit (x-axis), separated by treatment sequence (as specified above) for all anti-bimekizumab antibody positive subjects, including Baseline positive subjects.
- Box plots Plot of ADAb titer (logscale) by time to first ADAb positivity by treatment **sequence**.

For purposes of efficacy subgroup analyses based on anti-bimekizumab antibody status, two categories will be used:

- Anti-bimekizumab antibody positive – This is defined as subjects who have anti-bimekizumab antibody levels above the specified cut point on at least 2 time points while on treatment (ie, excluding Baseline, excluding SFU).
- Anti-bimekizumab antibody negative – Subjects who are not defined as anti-bimekizumab antibody positive (as described above) will be defined as anti-bimekizumab antibody negative.

The groups for defining anti-bimekizumab antibody status for safety subgroup analyses are as follows:

- AEs starting before first anti-bimekizumab antibody positive result
- AEs starting on or after first anti-bimekizumab antibody positive result
- AEs for subjects who were always anti-bimekizumab antibody negative

In addition to the anti-bimekizumab antibody classifications, subjects may also receive an overall neutralizing (NAb) classification for each NAb assay separately (**IL-17AA and IL-17FF**),

inclusive of Baseline and post-Baseline results, on the NAb assay results. **The classifications are as follows:**

- **NAb negative: No NAb positive samples at Baseline or post-Baseline and did not discontinue prior to Week 144. Subjects can have up to 1 missing sample.**
- **NAb positive: One or more positive samples (IL-17AA positive, IL-17FF positive, or both) at Baseline or post-Baseline (regardless of missing samples). Subjects who are NAb positive will be further classified as follows:**
  - **Positive for IL-17AA only: one or more positive samples for IL-17AA at Baseline or post Baseline. No positive samples for IL-17FF**
  - **Positive for IL-17FF only: one or more positive samples for IL-17 FF at Baseline or post Baseline. No positive samples for IL-17AA**
  - **Positive for both IL-17AA and IL-17FF: one or more positive samples for both IL-17AA and IL-17FF at Baseline or post Baseline**
- **NAb Missing: >1 relevant NAb samples are missing, eg, if subject had samples selected for NAb testing based on their anti-bimekizumab antibody levels, but there was insufficient sample left for NAb testing, or the subject discontinued prior Week 144 visit.**

**A summary table covering the initial, maintenance and OLE periods combined by treatment sequence will be produced, in addition, to summarize the NAb status overall.**

**A listing will be produced to summarize the NAb status by visit. The listing should be sorted by treatment sequence, subject identifier, and visit and would provide the following information for each subject:**

- **Visit**
  - **Study week since first BKZ dose**
  - **Sample date and time**
  - **Time since previous dose (weeks)**
- **NAb status and the corresponding bimekizumab plasma concentration (ug/mL) and the anti-bimekizumab antibody level titer at this visit**
- **IL-17AA NAb status and corresponding IL-17AA signal/negative control result  
IL-17FF NAb status and corresponding IL-17FF signal/negative control result**

**The tables will provide the following overall summary statistics by treatment group:**

- **Total number and percentage of anti-bimekizumab antibody positive, anti-bimekizumab antibody negative and missing subjects at each visit**
- **Number and percentage of subjects who are NAb positive, NAb negative and missing at each visit**
- **The number and percentage of subjects who are IL-17AA NAb positive, IL-17FF NAb positive, or both**

## Change #40

**Section 10.1 Extent of exposure:** The following texts in bold have been added:

For the **Week 144 analysis and for** the final analysis, the table will also be created for the BKZ set and will include the above categories plus the below categories. A bimekizumab total column will be displayed.

- $\geq 72$  weeks
- $\geq 96$  weeks
- $\geq 120$  weeks
- $\geq 144$  weeks

**In addition, the OLE2 exposure will be displayed as follow:**

- **>0 weeks**
- **$\geq 16$  weeks**
- **$\geq 24$  weeks**
- **$\geq 48$  weeks**

Throughout this section, date of last clinical contact for each subject is defined as the maximum of (last visit date including SFU **or** SFU2 visit, last imputed AE start date, date of study

## Change #41

**Section 10.1.4.1:** For subjects who do not switch study treatments

The number of days in (bold) added to the time at risk has been changed from 140 to 141

Time at risk (days)

Study medication duration (days)

- **For subjects who receive Q4W in the Open-Label Extension Period (subjects who discontinue prior to switching to Q8W):**
  - Date of last bimekizumab dose in the Open-Label Extension Period – date of first dose in the Open-Label Extension Period + 28 days (for subjects on Q4W dosing)
- **For subjects who receive Q8W in the Open-Label Extension Period use the minimum of:**
  - Date of last bimekizumab dose in the Open-Label Extension Period – date of first dose in the Open-Label Extension Period + 56 days
  - **First dose date in Open-Label Extension 2 Period – date of first dose in the Open-Label Extension Period + 1**

Note: If date of last bimekizumab dose in the Open-Label Extension Period + 28 days (or 56 days for subjects on Q8W dosing) extends to a date beyond the final visit date (including PEOT, but not including SFU), then this calculation reverts to:

- Final visit date (including PEOT, but not including SFU) – date of first dose in the Open-Label Extension Period+ 1.

Note: For subjects who die, if date of last bimekizumab dose in the Open-Label Extension Period + 28 days (or 56 days for subjects on Q8W dosing) extends to a date beyond the date of death, then this calculation reverts to:

- Date of death – date of first dose in the Open-Label Extension Period+ 1.

#### Time at risk (days)

- For all subjects, use the minimum of the following:
  - Date of last dose in the Open-Label Extension Period – date of first dose in the Open-Label Extension Period + 140 days,
  - Date of first dose in OLE2 - date of first dose in the Open-Label Extension Period + 1 day
  - Date of last clinical contact in OLE **and** SFU – date of first dose in the Open-Label Extension Period + 1.
  - Date of death – date of OLE first dose +1

#### **Change #42**

**Section 10.1.4.2:** For subjects who switch from BKZ 320mg Q4W to Q8W during Open-Label Extension Period

Following Protocol Amendment 5.0, subjects **receiving Q4W** should switch to Q8W during the Open-Label extension period. (see Section 2.3.2.4 for further details).

#### Study medication duration (days)

- Attributed to BKZ 320mg Q4W:
  - Date of last BKZ 320mg Q4W dose in the OLE Period – date of first BKZ 320mg Q4W dose in the OLE Period + 28 days

Note: If date of last BKZ 320mg Q4W dose in the OLE Period + 28 days extends to a date beyond the date of first BKZ 320mg Q8W dose in the OLE Period, then this calculation reverts to:

- Date of first BKZ 320mg Q8W dose in the OLE Period – date of first BKZ 320mg Q4W dose in the OLE Period + 1.

- Attributed to BKZ 320mg Q8W **use the minimum of:**
  - Date of last BKZ 320mg Q8W dose in the OLE Period – date of first BKZ 320mg Q8W dose in the OLE Period + 56 days.

- **First dose date in Open-Label Extension 2 Period – date of first BKZ 320mg Q8W dose in the Open-Label Extension Period+ 1.**

Note: If date of last bimekizumab dose in the Open-Label Extension Period + 56 days extends to a date beyond the final visit date (including PEOT, but not including SFU), then this calculation reverts to:

- Final visit date (including PEOT, but not including SFU) – date of first BKZ 320mg Q8W dose in the OLE Period + 1.

Note: For subjects who die, if date of last bimekizumab dose in the Open-Label Extension Period + 56 days extends to a date beyond the date of death, then this calculation reverts to:

- Date of death – date of first BKZ 320mg Q8W dose in the OLE Period + 1.

- **Attributed to Total BKZ**

- Sum of study medication duration in OLE period attributed to BKZ 320mg Q4W and study medication duration in OLE period attributed to BKZ 320mg Q8W - 1.

Time at risk (days)

- **Attributed to BKZ 320mg Q4W:**

- Date of first BKZ 320mg Q8W dose in the OLE Period – date of last BKZ 320mg Q4W dose in the OLE Period + 1 day

- **Attributed to BKZ 320mg Q8W:**

- For all subjects, use the minimum of the following:

- Date of last BKZ 320mg Q8W dose in the OLE Period – date of first BKZ 320mg Q8W dose in the OLE Period + 140 days.
- Date of first BKZ 320mg Q8W dose in OLE2 - date of first BKZ 320mg Q8W dose in the Open-Label Extension Period + 1 day
- Date of last clinical contact – date of first BKZ 320mg Q8W dose in the OLE Period + 1.
- **Date of death – date of first BKZ 320mg Q8W dose in the OLE Period + 1.**

- **Attributed to Total BKZ:**

- Use the time at risk algorithm specified for subjects who do not switch study treatments in Section [10.1.4.1](#)

**Change # 43**

**Section 10.1.5.1 For subjects who do not switch dose**

Time at risk (days)

- For all subjects, use the minimum of the following:
  - Date of last dose – date of first + 140 days.

- Date of last clinical contact – date of first dose + 1.
- **Date of death – date of first dose + 1.**

For subjects randomized to secukinumab at Baseline who initiate bimekizumab at Week 48 and continue on the same dose schedule in the OLE without switching, use the study medication duration and time at risk algorithms specified for subjects who do not switch study treatments in Section 10.1.4.1

#### Change #44

**Section 10.1.5.2:** For subjects who do not switch dose

The following texts (in bold) have been added:

##### Study medication duration (days)

Total study medication duration attributed to each dose will be obtained by summing the study medication duration(s) at each specific dose in each individual study period. Total study medication duration attributed to BKZ Total will be obtained by summing the study medication durations in each individual study period **and deducting n-1, where n is the number of periods covered that are being summed.**

- Attributed to BKZ 320mg Q8W
  - Date of last consecutive BKZ 320mg Q8W dose in current study period – date of first consecutive BKZ 320mg Q8W dose in current study period + 56 days

Note: If date of last consecutive BKZ 320mg Q8W dose in current study period + 56 days extends to a date beyond the date of first BKZ 320mg Q4W dose in the next study period, then this calculation reverts to:

- Date of first BKZ 320mg Q4W dose in the next study period – date of first BKZ 320mg Q4W dose in the current study period.

Note: If BKZ 320mg Q8W is the last dosing schedule received in the last study period the subject receives bimekizumab in and date of last consecutive BKZ 320mg Q8W dose in current study period + 56 days extends to a date beyond the final visit date (including PEOT, but not including SFU), then this calculation reverts to:

- Final visit date (including PEOT, but not including SFU) – date of first BKZ 320mg Q8W dose in the current study period + 1.

**Note: For subjects who progress into the OLE2, if date of last bimekizumab dose in the Open-Label Extension Period + 56 days extends to a date beyond the date of first dose in the Open-Label Extension 2 Period then this calculation reverts to:**

- **First dose date in Open-Label Extension 2 Period – date of first BKZ 320mg Q8W dose in the current study period + 1.**

Note: For subjects who die, where BKZ 320mg Q8W is the last dosing schedule received in the last study period the subject receives bimekizumab in and date of last consecutive BKZ

320mg Q8W dose in current study period+ 56 days extends to a date beyond the date of death, then this calculation reverts to:

- Date of death – date of first BKZ 320mg Q8W dose in the current study period + 1.

### Time at risk (days)

Total time at risk attributed to each dose will be obtained by summing the time(s) at risk at each specific dose in each individual study period **and deducting n-1, where n is the number of non-consecutive periods covered that are being summed**. Total time at risk attributed to BKZ Total will be obtained by using the time at risk algorithms specified for subjects who do not switch study treatments in Section 10.1.5.1.

- Time at risk at each specific dose in each individual study period is calculated separately as follows:
  - Attributed to BKZ 320mg Q4W:
    - Date of first BKZ 320mg Q8W dose in the next study period – date of first BKZ 320mg Q4W dose in the current study period.

Note: If BKZ 320mg Q4W is the last dosing schedule received in the last study period, then this calculation reverts to:

    - For all subjects, use the minimum of the following:
      - Date of last BKZ 320mg Q4W dose in the current study period – date of first BKZ 320mg Q4W dose in the current study period + 140 days.
      - Date of first BKZ 320mg Q8W dose in OLE2 - date of first BKZ 320mg Q4W dose in the Open-Label Extension Period + 1 day. The OLE and The OLE2 treatment periods should not overlap by more than 1 day
      - Date of last clinical contact – date of first BKZ 320mg Q4W dose in the OLE Period + 1.
      - **Date of death – date of first BKZ 320mg Q4W dose in the current study period + 1**
    - Attributed to BKZ 320mg Q8W:
      - Date of first BKZ 320mg Q4W dose in the next study period – date of first BKZ 320mg Q8W dose in the current study period.

Note: If BKZ 320mg Q8W is the last dosing schedule received in the last study period, then this calculation reverts to:

      - For all other subjects, use the minimum of the following:
        - Date of last BKZ 320mg Q8W dose in the current study period – date of first BKZ 320mg Q8W dose in the current study period + 140 days.
        - Date of first dose in OLE2 - date of first BKZ 320mg Q8W dose in the Open-Label Extension Period + 1 day.

- Date of last clinical contact – date of first BKZ 320mg Q8W dose in the OLE Period + 1.

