### **3.5.10 Bimekizumab Set**

The Bimekizumab Set (BKZ Set) consists of all randomized subjects who received at least 1 dose of bimekizumab in the double-blind or Open-Label extension treatment period.

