##### Time at risk (days)

- For all subjects, use the minimum of the following:
  - Date of last dose – date of first + 140 days.
  - Date of last clinical contact – date of first dose + 1.
  - Date of death – date of first dose + 1.

For subjects randomized to secukinumab at Baseline who initiate bimekizumab at Week 48 and continue on the same dose schedule in the OLE without switching, use the study medication duration and time at risk algorithms specified for subjects who do not switch study treatments in Section [10.1.4.1](#)

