#### Time at risk (days)

Total time at risk attributed to each dose will be obtained by summing the time(s) at risk at each specific dose in each individual study period and deducting n-1, where n is the number of non-consecutive periods covered that are being summed. Total time at risk attributed to BKZ Total will be obtained by using the time at risk algorithms specified for subjects who do not switch study treatments in Section 10.1.5.1.

- Time at risk at each specific dose in each individual study period is calculated separately as follows:

- Attributed to BKZ 320mg Q4W:

- Date of first BKZ 320mg Q8W dose in the next study period – date of first BKZ 320mg Q4W dose in the current study period.

Note: If BKZ 320mg Q4W is the last dosing schedule received in the last study period, then this calculation reverts to:

- For all subjects, use the minimum of the following:
- Date of last BKZ 320mg Q4W dose in the current study period – date of first BKZ 320mg Q4W dose in the current study period + 140 days.
- Date of first BKZ 320mg Q8W dose in OLE2 - date of first BKZ 320mg Q4W dose in the Open-Label Extension Period + 1 day. The OLE and The OLE2 treatment periods should not overlap by more than 1 day
- Date of last clinical contact – date of first BKZ 320mg Q4W dose in the OLE Period + 1.
- Date of death – date of first BKZ 320mg Q4W dose in the current study period + 1

- Attributed to BKZ 320mg Q8W:

- Date of first BKZ 320mg Q4W dose in the next study period – date of first BKZ 320mg Q8W dose in the current study period.

Note: If BKZ 320mg Q8W is the last dosing schedule received in the last study period, then this calculation reverts to:

- For subjects who die

Date of death – date of first BKZ 320mg Q8W dose in the current study period + 1.

For all other subjects, use the minimum of the following:

- Date of last BKZ 320mg Q8W dose in the current study period – date of first BKZ 320mg Q8W dose in the current study period + 140 days.
- Date of first dose in OLE2 - date of first BKZ 320mg Q8W dose in the Open-Label Extension Period + 1 day.
- Date of last clinical contact – date of first BKZ 320mg Q8W dose in the OLE Period + 1.

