- Listing of COVID-19 Vaccine Interval TEAEs

The following summaries will be provided for the BKZ Set by treatment at the time of AE onset. These tables will include AEs from both the double-blind and Open-Label treatment period (excluding OLE2 treatment period). AEs that occurred while subjects received secukinumab will not be included.

- Incidence of TEAEs Overview
- Incidence of TEAEs per 100 Subject-Years
- Incidence of Serious TEAEs per 100 Subject-Years
- Incidence of TEAEs by decreasing frequency of PT

- Incidence of TEAEs per 100 subject years by SOC, HLT, and PT and by Time of Onset Relative to COVID-19 pandemic (prior to COVID-19 pandemic, during COVID-19 pandemic).

In addition, all summaries of TEAEs based on “100 subject years” will include EAIR (with 95% CI) and EAER.

The following summaries will be presented for subjects who switched from secukinumab to bimekizumab at Week 48. The analyses will assign AEs according to the AE onset date relative to last secukinumab dose and accounting for approximately 5 times half-life (Onset  $\leq$  140 days from last secukinumab dose or Onset  $>$  140 days from last secukinumab dose):

- Incidence of TEAEs Overview
- Incidence of TEAEs per 100 Subject-Years
- Incidence of Serious TEAEs per 100 Subject-Years

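### Bimekizumab Set: for Q8W subjects who never enter the OLE, the last-contact limit on time at risk refers to an OLE dose they did not receive, so early losses are over-credited in the Q8W column

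*SAP*

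**What the plan says.** The Bimekizumab Set (SAP Section 3.5.10) "consists of all randomized subjects who received at least 1 dose of bimekizumab in the double-blind or Open-Label extension treatment period". It therefore includes subjects whose only bimekizumab exposure was in the double-blind period. Subjects who change interval are handled in Section 10.1.5.2, and a subject re-randomized from Q4W to Q8W at Week 16 is one of them.

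For such a subject, when Q8W is the last schedule received and the subject has not died, Section 10.1.5.2 takes the smallest of three quantities:

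- last Q8W dose minus first Q8W dose, both in the current study period, plus 140 days;
- first OLE2 dose minus first Q8W dose in the OLE, plus 1;
- "Date of last clinical contact – date of first BKZ 320mg Q8W dose in the OLE Period + 1".

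Deaths have their own rule, which starts at the first Q8W dose of the current study period.

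The column for all bimekizumab is derived separately for switchers: "Total time at risk attributed to BKZ Total will be obtained by using the time at risk algorithms specified for subjects who do not switch", with a reference to Section 10.1.5.1. In that section, subjects randomized to bimekizumab have the last-contact limit "Date of last clinical contact – date of first dose + 1".

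**The concern.** The first and third terms of the minimum should describe the same stretch of time, ended either by the 140-day window or by the last contact. They have different origins. A subject re-randomized to Q8W at Week 16 who stops before Week 48, or who completes Week 48 and does not enter the optional OLE, has no Q8W dose in the OLE. The last-contact term cannot be calculated for that subject, and the only quantity left is the 140-day term.

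The last-contact limit exists to stop the plan crediting time during which nobody was observing the subject. Without it, a subject lost soon after the last dose is treated as observed and event-free for up to 20 weeks. These times are the denominators of the exposure-adjusted incidence and event rates (Section 10.2.1), which Section 10.2.2 reports for the Bimekizumab Set by treatment at onset. Extra time in the Q8W denominator lowers the Q8W rates.

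**Working it through.** The SAP gives no figure for this point, so the check applies its date rules to an illustrative subject.

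**Inputs.** Subject randomized to bimekizumab, first dose at Week 0, Q8W from Week 16 (re-randomization, Section 2.3.2.3), last injection an active Q8W dose at Week 24 (an active visit in Table 7–1), never in the OLE. One week is 7 days. The date of last contact is varied. The safety follow-up visit is due 20 weeks after the last dose, here Week 44.

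**Q8W time as written (Section 10.1.5.2).**
- 140-day term: (24 − 16) × 7 + 140 = 56 + 140 = 196 days.
- OLE2 term: not applicable, because the subject cannot reach the OLE2.
- Last-contact term: undefined, because there is no OLE dose.
- Result: 196 days, whatever the last contact.

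**Q8W time with the last-contact term started at the first Q8W dose of the current period.** Last-contact term = (week of last contact − 16) × 7 + 1.

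| Last contact | Last-contact term | Minimum with 196 | Excess as written |
|---|---|---|---|
| Week 26 | 71 | 71 | 125 |
| Week 30 | 99 | 99 | 97 |
| Week 36 | 141 | 141 | 55 |
| Week 44 | 197 | 196 | 0 |

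**Check against the SAP's own total.** For the same subject, Section 10.1.5.1 gives the bimekizumab total as the smaller of 24 × 7 + 140 = 308 and (week of last contact) × 7 + 1. With last contact at Week 26 that is 183 days. The Q4W part under Section 10.1.5.2 is first Q8W dose minus first Q4W dose, 16 × 7 = 112 days. As written, the parts add to 112 + 196 = 308, which is 125 days more than the total. With the current-period origin they add to 112 + 71 = 183, which agrees with it.

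**Comparison with the parallel rule.** Section 10.1.2, which Section 10.1.3.2 uses for the Q8W part of the double-blind tables, starts its last-contact term at the first Maintenance dose. For a subject with last contact at Week 26 it gives 71 days, so the same subject has 71 days of Q8W time at risk in one table and 196 in another.

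**Ceiling for the whole set (assumptions, not SAP figures).** Two thirds of 350 is about 233; take about 230 subjects re-randomized to Q8W. If 8–15% do not reach the OLE, 18–34 subjects are concerned. The largest excess per subject is 139 days (last contact on the day of the last dose): 18 × 139 / 365.25 = 6.9 and 34 × 139 / 365.25 = 12.9, so at most about 7–13 patient-years.

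**The case against.** The case for leaving this alone has substance. The 140-day term still caps the time, and deaths follow a rule with the correct origin. Last clinical contact includes the safety follow-up visit, so a subject who attends it loses little or nothing, as the Week 44 row shows. Only Q8W subjects who never enter the OLE and are lost before that visit are affected, and the 7–13 patient-years would need every one of them to have been last seen on the day of the last dose. A careful programmer would probably use the current-period date unprompted. All of this limits the size. It does not make the written term calculable.

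Two stronger readings are tempting, and the SAP does not support them.

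*That these Q8W subjects have no upper limit, or no time at risk at all.* The rule is a minimum over several terms, and the 140-day term is correctly defined for them.

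*That secukinumab time enters the Bimekizumab Total.* A reader might infer this because Section 10.1.5.1 subtracts the date of first dose and its secukinumab clause is worded "For subjects randomized to secukinumab at Baseline who initiate bimekizumab at Week 48 and continue on the same dose schedule in the OLE without switching", whereas secukinumab subjects who start the OLE on Q4W are later moved to Q8W. If such a subject, with last dose at Week 136 and last contact at Week 156, were counted from Week 0, the time would be 136 × 7 + 140 = 1092 days. Counted from Week 48 it is 88 × 7 + 140 = 756 days, a gap of 336 days, although "AEs that occurred while subjects received secukinumab will not be included". But the first-dose formula is confined to subjects randomized to bimekizumab, for whom the first dose is a bimekizumab dose. Subjects randomized to secukinumab have their own branch, told to "use the study medication duration and time at risk algorithms specified for subjects who do not switch study treatments in Section" 10.1.4.1, which starts at the first OLE dose. Both branches are worded for non-switchers, and Section 10.1.5.2 deliberately applies them to switchers. Read consistently, each arm uses its own branch and no secukinumab time is counted. Section 10.1.4.2 borrows a non-switcher rule for its own total in the same way. What remains is that Section 10.1.5.2 does not say which branch applies to which switcher.

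**Conclusion.** The point holds as a drafting error with a small effect. For subjects in the Bimekizumab Set whose last schedule was Q8W in the double-blind period and who never entered the OLE, the last-contact limit is undefined. Those lost before the safety follow-up are over-credited by up to 139 days each. The consequence is a slight overstatement of Q8W-attributed time at risk and slightly low Q8W rates per 100 subject-years.

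The ceiling of about 7–13 patient-years rests on the assumed number re-randomized and the assumed 8–15% not reaching the OLE. The actual excess depends on how many are lost early and how soon, and should be well below it. The double-blind tables, the Bimekizumab Total column and the rule for deaths are not affected. The Q4W branch also uses an OLE origin, but under the planned sequences a switcher whose last schedule is Q4W reached it in the OLE, so that date exists.

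**What to change.** In Section 10.1.5.2, in the Q8W last-contact term, replace the reference to the OLE Period by the current study period, so that it has the same origin as the 140-day term beside it and follows the pattern of Section 10.1.2. For subjects whose last Q8W period is the OLE the two dates are the same, so their results do not change.

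As a clarification only, add a sentence to Section 10.1.5.2 stating that, for the Bimekizumab Total, switchers randomized to secukinumab use the algorithm of Section 10.1.4.1.

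Both are wording changes to the SAP. They need no new data and, at most, a one-line change in the exposure program. A useful programming check is that the Q4W and Q8W times of each double-blind-only switcher add up to that subject's total.
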